8.4.1 Schedule of Assessments

Table 1 Schedule of Assessments—Part A

Part A	Screening	Injection #1					Injection #2				End of Treatment ¹	Unscheduled Visit (PI discretion)
Visit Number:		Visit 1	Telephone Contact 1	Visit 2	Visit 3	Visit 4	Visit 5	Telephone Contact 2	Visit 6	Visit 7	Visit 8	
Scheduled Day/Week	Within 28 days	Baseline (Day 0)	Week 2 ± 2 days	Week 4 ± 7 days	Week 12 ± 7 days	Week 20 ± 7 days	Week 24 ± 7 days	Week 26 ± 2 days	Week 36 ± 7 days	Week 44 ± 7 days	Week 48 ± 7 days	
Scheduled Month (approximate)		--		~Month 1	~Month 3	~Month 5	~Month 6		~Month 9	~Month 11	~Month 12	
Written Informed Consent / Assent ²	X											
Inclusion/Exclusion Criteria Review	X	X										
Demographics	X											
Medical History	X											
Complete Physical Examination	X										X	X
Query Subject: How have you felt in the last 2 weeks?			X	X	X	X	X	X	X	X	X	X
Directed Physical Examination		X		X	X		X		X			
Prior or Concomitant Medication Review / Medical Procedures	X	X		X	X	X	X		X	X	X	X
Tanner Stage	X				X		X		X		X	X
Vital Signs ³	X	X		X	X	X	X		X	X	X	X
Weight	X	X		X	X	X	X		X	X	X	X
Height	X	X		X	X	X	X		X	X	X	X
Hand and Wrist X-ray	X						X				X	

¹ If a decision is made to continue into Part B, neither Part A Visit 7 nor the End of Treatment assessment will be completed and subjects will proceed directly to the start of Part B Visit 7 of the study. See the following Schedule of Assessment for Part B.

² Informed Consent/Assent may be signed within 28 days prior to the Baseline visit

³ Vital signs to be measured BEFORE any blood draws

Part A	Screening	Injection #1					Injection #2				End of Treatment ¹	Unscheduled Visit (PI discretion)	
Visit Number:		Visit 1	Telephone Contact 1	Visit 2	Visit 3	Visit 4	Visit 5	Telephone Contact 2	Visit 6	Visit 7	Visit 8		
Scheduled Day/Week	Within 28 days	Baseline (Day 0)	Week 2 ± 2 days	Week 4 ± 7 days	Week 12 ± 7 days	Week 20 ± 7 days	Week 24 ± 7 days	Week 26 ± 2 days	Week 36 ± 7 days	Week 44 ± 7 days	Week 48 ± 7 days		
Scheduled Month (approximate)		--		~Month 1	~Month 3	~Month 5	~Month 6		~Month 9	~Month 11	~Month 12		
Urine Pregnancy Test—females only		X					X				X	X	
Urinalysis	X			X			X				X	X	
Hematology	X			X			X				X	X	
Chemistry	X			X			X				X	X	
Hepatitis B antigen/Hepatitis C antibody	X												
Serum lipids - fasting	X	X											

Schedule of Assessments – Part A continued on next page

Table 1 Schedule of Assessments—Part A (continued)

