8.5 Safety Evaluation

8.5.1 Safety Parameters

Safety parameters to be measured/assessed include eligibility assessments, medical history, vital signs, physical examinations, clinical laboratory tests, and pregnancy tests. Any abnormal hematology, serum chemistry, serum lipid, or urinalysis parameters considered clinically significant by the Investigator will be captured as AEs.

Subjects will be monitored throughout the study for AEs, as well as for changes in clinical status, vital signs, and laboratory data. Any non-serious AEs occurring from the time the ICF and Assent forms, if required, are signed until just prior to receiving the first injection of study drug will be considered as non-TEAEs unrelated to study drug administration.

Serious adverse events (SAEs) that occur as a result of study-mandated procedures during the time period after the ICF and Assent forms are signed, as appropriate, but prior to receiving the first injection of study drug will be collected but not designated as TEAEs.

In order to evaluate changes in the acute (within two weeks of administration) and chronic hormonal responses associated with GnRH antagonist treatments over time, subjects (or their parents/guardians) will be asked two weeks (14 days \pm 2 days) after every study drug administration (by telephone contact), and at each scheduled visit, the following question(s):

- How have you felt in the last two weeks?

or alternatively (if the parent or guardian is answering on behalf of the subject)

- How has your child felt in the last two weeks?

Investigators will record any adverse events that are reported at that time.

In addition the investigators will categorize the more specific responses that have been identified in the table ([Table 4](#)), which are often associated with GnRH antagonist injectable treatments. If the subject (or parent/guardian) does not report any condition (within the last two weeks) that fits into the [Table 4](#) categories, the Investigator will check the response that no conditions associated with GnRH antagonists were reported (“NO”). If any of the conditions reported by the subject (or parent/guardian) fit into one (or more) of the categories, then the Investigator will check “YES” for each applicable category. This reported information will be collected by completing [Table 4](#):

Table 4 GnRH Antagonist Evaluations

Any GnRH antagonist conditions reported?	Yes/No
If the answer is “Yes”, please categorize as described below:	

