8.6.1 Screening Visit

Screening assessments will be performed during the 28-day Screening period and prior to the first injection, unless otherwise specified. During screening, the following procedures and evaluations will be performed:

1. Informed consent and assent (if required); may be signed up to 28 days prior to Baseline/Day 0
2. Inclusion/exclusion criteria
3. Demographics
4. Medical History
5. Vital signs – measured prior to any blood draws
6. Prior and concomitant medications
7. Physical Examination-complete
8. Tanner stage
9. Height and weight
10. X-ray of non-dominant hand and wrist
11. Urine for urinalysis, performed using dipstick supplied by Sponsor
NOTE: results must be evaluated before dosing
12. Blood samples for clinical laboratory assessments
 - Hematology and chemistry parameters as per [Appendix 13.1](#)
 - Serum lipids, fasting for ≥ 8 hours (water permitted)
 - Hepatitis B Surface Antigen (HBsAg) and hepatitis C antibody (HCBAb)
13. Blood samples for basal LH, FSH, testosterone/estradiol concentrations PRIOR to the GnRHa stimulation
14. Blood samples for basal leuprolide concentrations PRIOR to the GnRHa stimulation
15. GnRHa stimulation: aqueous leuprolide acetate 20 $\mu\text{g}/\text{kg}$ body weight administered SC
16. Blood samples for LH, FSH, testosterone/estradiol concentrations 30 \pm 5 minutes AFTER the GnRHa stimulation
17. Schedule/confirm next visit

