8.6.2 Part A, Visit 1 (Baseline, Day 0)—Injection #1

Day 0 Predose:

1. Evaluate hematology, chemistry and urinalysis results from Screening Visit
2. Inclusion/exclusion criteria – review to verify that subject continues to meet all of the inclusion and none of the exclusion criteria.
3. Physical Examination-directed

4. Prior and concomitant medications
5. Vital signs – measured prior to any blood draws
6. Height and weight
7. Urine pregnancy test, females only
NOTE: Results must be negative prior to receiving study drug injection
8. Serum lipids, fasting for ≥ 8 hours (water permitted)
9. Blood samples for basal LH, FSH, testosterone/estradiol concentrations ≥ 30 minutes before planned injection time
10. Predose blood sample for serum leuprolide concentrations ≥ 30 minutes before planned injection time
11. Record all non-treatment emergent AEs from the time of informed consent/assent until first study drug administration

Day 0 Study Drug administration:

12. Pharmacy - prepare study drug for injection (see Pharmacy Manual for complete instructions)
 - a. Remove kit from refrigerator at least 30 minutes prior to planned administration and allow the study drug to reach room temperature
 - b. Start mixing process with the product kit within ≤ 30 minutes prior to the injection time.
13. Apply topical or local anesthetic (per Investigator discretion) to injection site prior to planned injection time; record medication, dose, route, and time
14. Administer first injection of study drug

Day 0 Postdose:

15. Blood sample for LH, FSH, testosterone/estradiol, and serum leuprolide concentrations post study drug injection time:
 - a. 1 hour \pm 5 minutes
 - b. 4 hours \pm 10 minutes
 - c. 6 hours \pm 15 minutes
16. Final AE assessment prior to subject discharge from clinic
17. Schedule/confirm next visit

8.6.3 Telephone Contact 1(14 days \pm 2 days):

1. Query subject or parent: “How have you felt in the last two weeks?” or “How has your child felt in the last two weeks?” Complete [Table 4](#)

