8.6.4 Part A, Visit 2 (~Month 1/Week 4 \pm 7 days)

1. Query subject or parent: “How have you felt in the last two weeks?” or “How has your child felt in the last two weeks?” Complete [Table 4](#)
2. Vital signs - measured prior to any blood draws
3. Physical Examination—directed
4. AE and concomitant medications assessments
5. Height and weight
6. Clinical laboratory assessments (hematology, chemistry) as per [Appendix 13.1](#)
7. Urine for urinalysis, performed using dipstick supplied by Sponsor

8. Blood samples for basal LH, FSH, testosterone/estradiol concentrations
9. Blood sample for basal serum leuprolide concentrations
10. Schedule/confirm next visit

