Hematology	X			X			X				X	X
Chemistry	X			X			X				X	X

 If a decision is made to continue into Part B, neither Part A Visit 7 nor the End of Treatment assessment will be completed and subjects will proceed directly to the start of Part B Visit 7 of the study. See the following Schedule of Assessment for Part B.

 Informed Consent/Assent may be signed within 28 days prior to the Baseline visit.

 Vital signs are to be measured BEFORE any blood draws.

Part A	Screening	Injection #1					Injection #2				End of Treatment 	Unscheduled Visit (PI discretion)
Visit Number:		Visit 1	Telephone Contact 1	Visit 2	Visit 3	Visit 4	Visit 5	Telephone Contact 2	Visit 6	Visit 7	Visit 8	
Scheduled Day/Week	Within 28 days	Baseline (Day 0)	Week 2 ± 2 days	Week 4 ± 7 days	Week 12 ± 7 days	Week 20 ± 7 days	Week 24 ± 7 days	Week 26 ± 2 days	Week 36 ± 7 days	Week 44 ± 7 days	Week 48 ± 7 days	
Scheduled Month (approximate)		--	~Month 0.5	~Month 1	~Month 3	~Month 5	~Month 6	~Month 6.5	~Month 9	~Month 11	~Month 12	
Hepatitis B antigen/Hepatitis C antibody	X											
Serum lipids – fasting	X	X										

Table 1 Schedule of Assessments—Part A (continued)

Part A	Screening	Injection #1					Injection #2				End of Treatment 	Unscheduled Visit (PI discretion)
Visit Number:		Visit 1	Telephone Contact 1	Visit 2	Visit 3	Visit 4	Visit 5	Telephone Contact 2	Visit 6	Visit 7	Visit 8	
Scheduled Day/Week	Within 28 days	Baseline (Day 0)	Week 2 ± 2 days	Week 4 ± 7 days	Week 12 ± 7 days	Week 20 ± 7 days	Week 24 ± 7 days	Week 26 ± 2 days	Week 36 ± 7 days	Week 44 ± 7 days	Week 48 ± 7 days	
Scheduled Month (approximate)		--	~Month 0.5	~Month 1	~Month 3	~Month 5	~Month 6	~Month 6.5	~Month 9	~Month 11	~Month 12	
LH and FSH samples (basal)	X	See Table 2		X	X	X	X		X	X	X	X
Testosterone/estradiol samples (basal)	X	See Table 2		X	X	X	X		X	X	X	X
Serum Leuprolide samples (basal) 	X	See Table 2		X	X	X	X		X	X	X	X
GnRH a Stimulation (SC leuprolide acetate) 	X				X		X		X		X	X

 If a decision is made to continue into Part B, neither Part A Visit 7 nor the End of Treatment assessment will be completed and subjects will proceed directly to the start of Part B Visit 7 of the study. See the following Schedule of Assessment for Part B.

 Blood samples for leuprolide serum concentrations must be collected BEFORE the GnRHa stimulation test.

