Baseline	Demographics (continuous)		x				Screening
Baseline	Medical History (categorical)	x					Screening
Baseline	Medical History (descriptive)					x	Screening
Baseline	Meds/Treatments History					x	Screening
Baseline, Safety	Vital Signs		x				Screening, All Visits
Baseline, Safety	Weight		x				Screening, All Visits
Baseline, Efficacy	Height		x				Screening, All Visits
Baseline, Safety	Complete Physical Exam (categorical)	x					Screening, Visit 11
Baseline, Safety	Complete Physical Exam (descriptive)					x	Screening, Visit 11
Safety	Directed Physical Exam (categorical)	x					Visits 1, 2,3,5,6,7,8, 9 10
Safety	Directed Physical Exam (descriptive)					x	Visits 1, 2,3,5,6,7,8, 9 10

 All collected and derived variable values will be in listings. However, this column highlights information that is closely related to information found in an adjacent row of this table; will not be descriptively analyzed; but will be presented in a listing.

 This table assumes that Part B will be invoked. If Part B is not invoked visits will be altered to conform to the *Schedule of Assessments: Part A*.

Variable Class	Variable(s)	Analysis				Listed/Not Analyzed 	Time Points Analyzed (Visits) 
		Categorical Descriptive Analysis	Continuous Descriptive Analysis	Shift Table Analysis	PK Analysis		
Safety	Flare Symptoms	x	x 				Telephone interview weeks 26 & 46, Visits 2-11
Safety	Pregnancy Test	x					Visits 1, 5,7, 9, 11
Safety	Adverse Events	Reported in Listings and Summarized in Tabulations 					Throughout Study
Baseline, Safety	Laboratory Tests 	x	x	x			Screening, All Visits
Baseline	Hepatitis B/C Antibody	x		x			
Baseline, Safety	Serum Lipids (fasting)	x	x				Screening, Visits 1,7
Efficacy	Leuprolide, LH, FSH, Testosterone, Estradiol (basal)		x		x		Screening, All Visits
Efficacy	LH, FSH, Testosterone, Estradiol (GnRHa stimulation) 	x	x				Screening, All Visits
PK	Serum Leuprolide (basal)		x		x		Screening, All Visits
Efficacy	Tanner Staging  and Menses Presence or Change	x	x	x			Screening, Visits 3, 5, 7, 8, 9, 10, 11
Efficacy	All Exploratory Efficacy Endpoints 	x	x				Screening, All Visits

 See Appendix 3: Global Interview Symptom Assessment. Each item will be analyzed separately using categorical descriptive analysis. A count of total number of symptoms will be analyzed using continuous descriptive analysis.

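### If Part B is not invoked, no dosed child has a scheduled on-treatment fasting lipid value, so two planned laboratory outputs cannot be produced for lipids

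*Protocol*

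**What the plan says.** The Protocol and the SAP give the same schedule. In Table 1 of each, the Part A lipid row ("Serum lipids - fasting" in the Protocol, "Serum lipids – fasting" in the SAP) is marked at Screening and Visit 1 only.

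- **Screening (Protocol 8.6.1).** "Screening assessments will be performed during the 28-day Screening period and prior to the first injection", unless otherwise specified; fasting lipids are one of those assessments.
- **Visit 1 (Protocol 8.6.2).** "Serum lipids, fasting for ≥ 8 hours (water permitted") is item 8 of the predose list. The injection is item 14. After the injection the bloods are "Blood sample for LH, FSH, testosterone/estradiol, and serum leuprolide concentrations post study drug injection time", with no lipids.
- **Part B Visit 7 (Protocol 8.6.12 and Table 3).** Fasting lipids are drawn before Injection #3. This is the only lipid draw in Part B.

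The plan also uses lipids as a safety measure. Protocol 8.5.1 says: "Any abnormal hematology, serum chemistry, serum lipid, or urinalysis parameters considered clinically significant by the Investigator will be captured as AEs". SAP Table 5 classes fasting lipids as both a baseline and a safety variable, with time points "Screening, Visits 1,7". A footnote to that table says it assumes Part B is run and that the visits otherwise follow the Part A schedule.

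**The concern.** A safety variable needs a value after exposure. Under Part A alone, lipids have two values before treatment, at most about 28 days apart, and none after it. Two outputs that the plan describes in general terms then have no lipid data behind them:

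- Protocol 9.2.6 will report laboratory tests that are normal at Screening and become abnormal during treatment.
- SAP 14.5 will plot baseline against end of study for every clinical laboratory parameter. SAP 8.1.9 and SAP Appendix 2 count fasting lipids among the clinical laboratory assessments.

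Protocol 6.2 notes that this formulation has not been given to children, and safety is a secondary objective. Children would fast and give blood twice for a parameter that is then not followed up.

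**Working it through.** This is a question of scheduling, so the check is a count of scheduled lipid draws by visit and by position relative to dosing.

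| Visit | Safety bloods listed | Lipids? | Position |
|---|---|---|---|
| Screening | hematology, chemistry, lipids, hepatitis | yes | before Injection #1 |
| Visit 1, predose | lipids | yes | before Injection #1 |
| Visit 1, postdose | none (hormones and leuprolide only) | no | after |
| Part A Visits 2, 5, 8 and Unscheduled | hematology, chemistry | no | after |
| Part A Visits 3, 4, 6, 7 | none | no | after |
| Part B Visit 7 (Month 11) | hematology, chemistry, lipids | yes | after two injections |
| Part B Visits 8, 10 | none | no | after |
| Part B Visits 9, 11 | hematology, chemistry | no | after |

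**Could the later chemistry panels include lipids?** The Visit 2 entry reads "Clinical laboratory assessments (hematology, chemistry) as per" Appendix 13.1, and Visits 5 and 8 use the same form. That appendix puts lipids in a separate group of other parameters, outside hematology and clinical chemistry. Screening and Part B Visit 7 name lipids on their own line. The later panels therefore do not cover them.

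**Could this be a broken table?** No. Protocol Table 1, SAP Table 1 and the visit lists in Protocol 8.6 all agree.

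**Counts per child completing the path**

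- Part A only: 2 draws = 2 before the first dose + 0 on treatment.
- Parts A and B: 3 draws = 2 before the first dose + 1 on treatment (Month 11), with 0 at end of study (Month 21).

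Part A Visit 7 and Part B Visit 7 are alternatives (Protocol 8.6.10). Without Part B the Month 11 draw does not occur, and under its footnote SAP Table 5 is left with Screening and Visit 1.

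**How likely is the Part A path?** Part B is avoided if at least 85% of the first 16 or so children are suppressed. Since 13/16 = 81.3% and 14/16 = 87.5%, this needs 14 or more of 16. Take 16 independent children with the plan's expected suppression rates of 85% and 90% (Protocol 9.1, SAP 6.7):

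P(X ≥ 14) = p^16 + 16·p^15·(1−p) + 120·p^14·(1−p)^2

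- p = 0.85: 0.074 + 0.210 + 0.277 = 0.56
- p = 0.90: 0.185 + 0.329 + 0.275 = 0.79

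Under these assumptions the branch with no on-treatment lipid value is the more likely one, but Part B still has a probability of about 0.44 or 0.21.

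**The case against.** The strongest reply is that nothing here is inconsistent at the level of the schedule. The Protocol and SAP tables agree, and SAP Table 5 labels lipids as baseline as well as safety. It also marks no shift table for lipids, although it does for the other laboratory tests. The documents name no lipid effect of the drug as a concern, no efficacy endpoint uses lipids, and with a single arm a later value would only be descriptive. All of this stands, and it keeps the point small. It does not remove the conflict with Protocol 9.2.6 and SAP 14.5, which are written for laboratory results in general and make no exception for lipids.

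A reader might infer three stronger things that the documents do not support.

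- **That a lipid abnormality on treatment could not be detected at all.** Tests outside the schedule are not forbidden, all adverse events must be reported (Protocol 8.5.5), and SAP 12.2 provides for listing unscheduled results. The Unscheduled Visit list does not name lipids, however. The supportable statement is that scheduled testing would not detect it.
- **That 0 of about 60 children would have a post-dose value.** The zero is right for scheduled draws. But the synopsis gives about 60 as the number screened and/or enrolled, and Protocol 8.6 counts a child as enrolled at consent and numbering. The number dosed is not given.
- **That Part B is so unlikely that only Part A matters.** Protocol 6.2 treats incomplete suppression at 6 months as improbable, but the plan's own expected rates leave Part B a substantial chance.

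**Conclusion.** The point holds as a gap between the assessment schedule and the safety outputs. If Part B is not invoked, no dosed child has a scheduled on-treatment lipid value, and neither the report of normal-to-abnormal changes (Protocol 9.2.6) nor the baseline against end-of-study plot (SAP 14.5) can be produced for lipids. If Part B is invoked, children who reach Part B Visit 7 (about 27 are expected to take part) have one on-treatment value at Month 11. None has a Month 21 value, so the SAP 14.5 plot fails for lipids on that path too.

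This rests on two readings: that clinical laboratory parameters in SAP 14.5 include lipids, as SAP 8.1.9 implies, and that on-treatment value means a scheduled one. The point is a cheap improvement to safety description. It has no bearing on the efficacy claim or the sample size.

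**What to change.** 1. Keep the Screening lipid draw as baseline and move the Visit 1 draw to Part A Visit 8 (End of Treatment or Early Discontinuation), where hematology and chemistry are already taken. Visit 5 is not an equal alternative: it would give an on-treatment value but not the end-of-study value that SAP 14.5 needs.
2. If Part B runs, the Visit 7 draw supplies the on-treatment value. Either move it to Visit 11, or keep it and state in the SAP that the Month 11 value serves as the last lipid value in place of an end-of-study one.
3. Update Protocol Table 1 and the visit lists, and SAP Tables 1 and 5. If the Part B draw moves, change Table 3 in both documents as well. A lipid shift table would be an optional addition, since none is planned now.

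The cost is a minor amendment. On the Part A path the number of draws stays at two (one before treatment, one after). On the Part B path it falls from three to two. The losses are the second baseline value, for which the documents give no reason, and some convenience, because the child must fast at a later visit.

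If the schedule can no longer be changed, label lipids as baseline-only where Part B is not run and exempt them from the Protocol 9.2.6 and SAP 14.5 outputs. Where Part B is run, exempt them from the SAP 14.5 plot or name the Month 11 value as the one plotted.

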8.6.4 Part A, Visit 2 (~Month 1/Week 4 \pm 7 days)

1. Query subject or parent: “How have you felt in the last two weeks?” or “How has your child felt in the last two weeks?” Complete [Table 4](#)
2. Vital signs - measured prior to any blood draws
3. Physical Examination—directed
4. AE and concomitant medications assessments
5. Height and weight
6. Clinical laboratory assessments (hematology, chemistry) as per [Appendix 13.1](#)
7. Urine for urinalysis, performed using dipstick supplied by Sponsor

8. Blood samples for basal LH, FSH, testosterone/estradiol concentrations
9. Blood sample for basal serum leuprolide concentrations
10. Schedule/confirm next visit

8.6.5 Part A, Visit 3 (~Month 3/Week 12 ± 7 days)

1. Query subject or parent: “How have you felt in the last two weeks?” or “How has your child felt in the last two weeks?” Complete [Table 4](#)
2. Vital signs - measured prior to any blood draws
3. AE and concomitant medications assessments
4. Physical Examination—directed
5. Tanner stage
6. Height and weight
7. Blood samples for basal LH, FSH, testosterone/estradiol concentrations PRIOR to the GnRHa stimulation
8. Blood sample for basal serum leuprolide concentrations PRIOR to the GnRHa stimulation
9. GnRHa stimulation: aqueous leuprolide acetate 20 µg/kg body weight administered SC
10. Blood samples for LH, FSH, testosterone/estradiol concentrations 30 ± 5 minutes AFTER the GnRHa stimulation
11. Schedule/confirm next visit

NOTE: Subjects who do not show adequate suppression of LH concentration to <4 mIU/mL (after GnRHa stimulation test) will be discontinued.

8.6.6 Part A, Visit 4 (~Month 5/Week 20 ± 7 days)

1. Query subject or parent: “How have you felt in the last two weeks?” or “How has your child felt in the last two weeks?” Complete [Table 4](#)
2. Vital signs
3. Height and weight
4. AE and concomitant medications assessments
5. Blood samples for basal LH, FSH, testosterone/estradiol concentrations
6. Blood sample for basal serum leuprolide concentrations
7. Schedule/confirm next visit

